## **"Comparison of Two Techniques of Combination Therapy for Treatment of OSA "**

### **Purpose of the study and background**

#### **• Purpose of the study**

To compare two techniques of combination therapy for obstructive sleep apnea (OSA) and determine if clinical data obtained before, during and after suggests that either or both techniques improve tolerance to CPAP and/or are statistically more efficacious than CPAP or oral appliance therapy alone.

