An alternative option for the treatment of SOB is oral appliance therapy (OAT). The AASM and the American Academy of Dental Sleep Medicine (AADSM) have provided management guidelines for the utilization of oral appliance therapy (14, 15). Although not as efficacious as CPAP, OAT is indicated for use in patients with mild to moderate OSA who prefer OAT to CPAP, or who do not respond to CPAP, are not candidates for CPAP, or who fail CPAP or behavioral measures such as weight loss or sleep position change. (15) OAT has also demonstrated cardiovascular benefits by lowering blood pressure and reducing mortality (16, 19). OAT has also been shown to have a good adherence rates as determined by mean hours of usage. One example of this is a study by Lowe and others showed an 'index of agreement' of 0.99 between the monitor clock time and the subject's log sheets. In the study, the mean hours of wear was 6.8 hours. (17)

While the benefits and good adherence of OAT are recognized, the efficacy of OAT remains less than optimal (partial response). Using a definition of decreasing Apnea-Hypopnea Index (AHI) to less than or equal to 10, it has been shown that the percent success rates for OAT was: Mild OSA-81%, Moderate OSA-60% and Severe OSA-25%. The mean success rate of OAT was 52% (18).

It would seem prudent that the simultaneous use of both CPAP and OAT (combination therapy) may be beneficial to consider. One pilot study has shown that combination therapy can reduce CPAP pressure (as compared to original PAP titration study) and improve effectiveness of OAT (20). Another study was able to show that OAT could be a short-term alternative to CPAP (21). The study demonstrated that an oral appliance could be as successful, or near successful as CPAP, and as being a convenient option for travel purposes.

There are two primary ways to use combination therapy. One way uses the oral appliance as an anchor for a customizable nasal mask interface (CNMI) while another way uses the patient's preferred CPAP mask separate from the oral appliance. This study will prospectively and randomly assign patients to one of the two combination therapy options and they will use each one for two months. Clinical data obtained during the study will be at one month and at the end of two months and will include: AHI, CPAP pressure, and mask leakage, Nadir, T90, hours of usage and ESS.

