### **Criteria for Subject Selection**

- Number of subjects: 50-100
- Gender of Subjects: Male and female with attempt of equal participation
- Age of Subjects: 18 and older
- Racial and Ethnic Origin: Distribution will mirror that of normal patient base of the clinics which is primarily Hispanic.
- Inclusion Criteria: Diagnosis of OSA with AHi greater than or equal to 5, CPAP intolerance due to CPAP pressure too high, mask fit/leak, Oral Appliance Therapy partial responders of AHi at or above 5, patients demonstrated successful adherence to oral appliance therapy.
- Exclusion Criteria: Daily use of alcohol, CNS depressants and narcotics, pregnancy and prisoners

- Vulnerable Subjects: Ethnic minorities and economically disadvantaged

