## Methods and Procedures

At least fifty patients who were intolerant to CPAP and had a partial response to OAT (AHI greater than or equal to 5 will be recruited randomly and prospectively into one of two groups (at least 25 each in each group). The group options were: 1} Combination therapy with CNMI and 2) Combination therapy with patient's preferred CPAP mask.

These CPAP intolerant patients underwent a PAP titration during an overnight PSG or were assigned an autoPAP and had accumulated at least one month of data. Intolerance to CPAP was defined as patients who reported to their sleep physician that they were intolerant due to CPAP pressure, mask fit/leak issues. They were also asked to fill out a CPAP intolerance questionnaire to document the reason for the intolerance.

Patients who were determined to be partial responders to OAT were determined to have met an adherence and titration protocol. Adherence was defined as using the oral appliance for at least 4 hours per night for 70% of the nights in the 30-day period leading up to the study. The titration protocol includes a minimum of one month of titration along with using patient testimony, bed partner testimony and overnight oximetry to aid in the titration and when tested with an HST or in-lab PSG, the AHI was greater than or equal to 5 (verification sleep test).

Patients who were assigned the option of using their previously preferred CPAP mask, they underwent one CPAP care session and then the two month time period would begin.

If patients were assigned the CNMI option, they were allowed one week for follow up/adjustments of the customized mask, they also underwent one CPAP care session and then the two month time period would begin.

► Data Analysis and Data Monitoring - Data will be analyzed quantitatively using, but not limited to, the Kolmogorov-Smirnov test, Student's *t* test or the Wilcoxon rank- sum test, and SPSS 12.0 for Windows {Chicago, IL, USA}).

Demographic: Ask patients for age and gender

Physiologic: Weight Scale - Weight+ Ruler - Height= Body mass index (BMI)

Pulse Oximeter: Nadir (low O2 saturation), Time percent below 90 {T90}

Polysomnography {PSG}: Apnea-Hypopnea Index (AHI), CPAP pressure, leakage

CPAP Airview or Data Card: AHI, CPAP pressure, leakage

Home Sleep Study (HST): AHI, Nadir, and T90

► Data Monitoring - At time of start of study at [name] Dental Sleep Medicine, PLLC or at J. [name], P.A. Obtain from patient:

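### Superiority over CPAP alone or oral appliance alone is a stated purpose, but only the two combination techniques are randomised; the monotherapy contrasts are uncontrolled before-after comparisons

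*Combined protocol and SAP*

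**What the plan says.** The Purpose of the study has two parts: to compare two ways of combining CPAP with an oral appliance, and to judge whether "clinical data obtained before, during and after suggests that either or both techniques improve tolerance to CPAP and/or are statistically more efficacious than CPAP"; the second comparator is the oral appliance on its own. It says the evidence is data from before, during and after treatment.

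Methods and Procedures defines two groups: "The group options were: 1} Combination therapy with CNMI and 2) Combination therapy with patient's preferred CPAP mask". The Background says the study will "randomly assign patients to one of the two combination therapy options and they will use each one for two months".

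The monotherapy data are as follows.

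- **CPAP alone:** patients "underwent a PAP titration during an overnight PSG or were assigned an autoPAP and had accumulated at least one month of data".
- **OAT alone:** partial responders are those for whom, "when tested with an HST or in-lab PSG, the AHI was greater than or equal to 5 (verification sleep test").

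The Data Monitoring lists collect CPAP data (titration or autoPAP) and a home sleep test (HST) at the start. At months 1 and 2 they collect device data (Airview or data card) and pulse oximetry, with PSG or HST optional. Both groups have one CPAP care session before the two months begin. The planned size is "Number of subjects: 50-100", with a minimum of 25 per group. The analysis text lists general tests without linking any of them to a contrast.

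**The concern.** One stated purpose is a statistical superiority claim over two comparators that no patient receives alone during the study. The plan discloses the before-after basis, but nothing labels these contrasts exploratory or limits how a significant change may be described. A change from baseline could then be reported as superiority over CPAP or OAT although part of it may come from patient selection, the care session or a change of measuring instrument. The direction of an instrument offset is not known, so it could equally hide a real benefit.

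**Working it through.** **1. Is there a monotherapy arm or period?** Both options in Methods and Procedures are combination therapy. The Background phrase about using each one for two months can be read as parallel groups or as a crossover. In a crossover each patient would use both combination techniques, and still neither CPAP alone nor OAT alone. Under either reading the only randomised contrast is CNMI versus preferred mask.

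**2. Does any passage limit the inference?** The Purpose uses the softer verb suggests, but its object is statistical superiority. The benefit statement under Risk/Benefit Assessment speaks only of a possibility of helping subjects. No section calls the monotherapy contrasts exploratory or descriptive.

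**3. What else differs between before and after?** The Background promises "AHI, CPAP pressure, and mask leakage, Nadir, T90, hours of usage and ESS" on study. The sources below are those in Methods and Procedures and the Data Monitoring lists.

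| Contrast or measure | Before | Months 1 and 2 | Like for like? |
|---|---|---|---|
| AHI against OAT alone | HST or PSG | Device; PSG/HST optional | Only where the optional test is done and is of the same type |
| AHI, pressure, leakage against CPAP alone | Titration PSG or autoPAP | Device | Yes with an autoPAP baseline; no with a titration PSG |
| Nadir, T90 | HST or CPAP data | Pulse oximeter | Listed sources differ |
| CPAP intolerance questionnaire | Yes | Yes | Yes, but exposed to the care session |

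The start list also has a separate autoPAP entry for AHI and mask leakage. It does not say whether this covers all patients, so the number of device pairs is unknown.

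**4. Which influence bears on which contrast?**
- *Selection* bears on both contrasts: patients enter because they report CPAP intolerance and because AHI on OAT is 5 or more.
- *The care session* bears mainly on CPAP and tolerance. For the OAT contrast, adding CPAP is the intervention, and setting it up is arguably part of it.
- *Instrument change* bears mainly on OAT AHI and on Nadir/T90. It also affects the CPAP contrast for patients with a titration-PSG baseline.

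**5. Scale.** The plan's own arithmetic agrees: 2 × 25 = 50, the lower bound. There is no power calculation to reproduce and no SD. The following is illustrative only and assumes a two-sided 0.05 paired t test, near-normal differences and no treatment effect. An offset equal to the 95% half-width, t(0.975, n−1)/√n, gives about a 50% chance of significance:

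- n = 25 (one group): 2.064/5 = 0.41 SD of the paired difference
- n = 50: 2.010/7.071 = 0.28 SD
- n = 100: 1.984/10 = 0.20 SD

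The 80% points (noncentral t) are 0.58, 0.40 and 0.28 SD. These figures say how large an offset would have to be, not that one exists. The plan names no paired test, and a rank test or skewed data would change the chance.

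For regression to the mean under a normal model, the expected fall is (1 − ρ)·φ(c)/p, where p is the fraction passing the entry cut-off c. Assuming p = 0.50 to 0.75 and ρ = 0.5 to 0.9:

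- largest: (1 − 0.5) × 0.399/0.50 = 0.40 SD of the unselected AHI
- smallest: (1 − 0.9) × 0.318/0.75 = 0.04 SD

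The tenfold range comes entirely from the assumed inputs. The effect applies to the OAT baseline only if the start HST is the qualifying test; a fresh HST would remove it.

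**The case against.** The strongest reply is that the design is disclosed. The title and the Purpose put the technique comparison first, the before-after basis is stated, and paired within-patient estimates are legitimate in a small study. That stands, and it is why the estimates should be kept. It does not license the superiority wording.

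Several other points also stand.

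- The baseline on OAT is reasonably settled. Patients need at least a month of titration and use for at least 4 hours on 70% of nights over the preceding 30 days, so drift on OAT alone is less likely.
- The CNMI group's adjustment week may not distinguish the groups much, because Risk/Benefit Assessment promises patients generally a follow-up within a week of delivery.
- Overnight oximetry is used during OAT titration, so matching oximeter data may exist, although the start list does not collect it.
- No document shows that an instrument offset exists.

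A reader might go further and infer that the monotherapy contrasts are worthless, that any AHI fall would be artefact, or that a monotherapy arm is required. The documents do not support this. Nothing in them suggests that selection or instrument change could produce a large fall against OAT alone. Nor should every cross-instrument comparison be dropped: because follow-up PSG/HST is optional, that could remove most or all of the OAT AHI contrast.

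**Conclusion.** The concern holds in a limited form. The stated inference, statistical superiority over CPAP alone or OAT alone, is one the design cannot support, because both groups receive combination therapy and no section restricts the claim. This follows from the text and does not depend on the illustrative figures. The consequence is mainly for small to moderate changes. The size of any distortion cannot be given in events per hour: the documents supply no SD, no reliability, no instrument offset and no care-session effect. The SD-unit figures rest on an assumed paired t test, and the regression-to-the-mean range on assumed inputs. The point should be fixed before results are reported.

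**What to change.** 1. Restate the Purpose. The randomised comparison is CNMI versus preferred mask. Contrasts with CPAP alone and OAT alone are exploratory paired estimates with 95% confidence intervals, with no claim of statistical superiority.
2. Report same-instrument pairs separately wherever they exist: device with autoPAP device, HST with HST, PSG with PSG. Give the number of patients for each. Label results from optional tests as a non-random subset.
3. Keep the cross-instrument contrasts (OAT-alone HST or PSG AHI against device AHI; Nadir and T90), but report them descriptively. Do not pool instruments.

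No new arm or measurement is needed. The cost is a weaker headline and less precision in the like-for-like subsets. For example, if 30–70% of 50 patients had an autoPAP baseline (assumed), 15 to 35 device pairs would remain. The 95% half-width would grow from 0.28 SD to between 2.032/√35 = 0.34 SD and 2.145/√15 = 0.55 SD. For OAT AHI the loss may be greater: same-instrument pairs depend on an optional test, so there could be very few or none, and that contrast might then be descriptive only.

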- 1) CPAP intolerance questionnaire
- 2) Compliance questionnaire with oral appliance
- 3) Obtain CPAP data from PAP titration or autoPAP: CPAP pressure, Leakage, Apnea-Hypopnea Index (AHi), Nadir, Time percent below 90 (T90), hours of usage
- 4) Home Sleep Test (HST): AHi, Nadir, T90
- 5) AutoPAP: AHi, mask leakage
- 6) Gather patient demographics: age, gender, BMI

At one (1) Month

- 1) CPAP intolerance questionnaire
- 2) Compliance questionnaire with Oral Appliance
- 3) Gather CPAP data from "Airview" or Data card: CPAP pressure, leakage, AHi,
- 4) Gather oxygen saturation data from Pulse Oximeter: Nadir and T90
- 5) Optional verification (PSG or HST)

After 2nd Month

- 1) CPAP intolerance questionnaire
- 2) Compliance questionnaire with Oral Appliance
- 3) Gather CPAP data from "Airview" or Data card: CPAP pressure, leakage, AHi,
- 4) Gather oxygen saturation data from Pulse Oximeter: Nadir and T90
- 5) Optional verification (PSG or HST)

- Data Storage and Confidentiality- Data will be safeguarded by assigning study participants anonymous identification numbers. Depending on relevant data, it will be stored in a password protected computer with encrypted files in the sleep lab at the Pulmonary & Sleep Center of the Valley to which sub-investigator, [name] may access. At [name], D.D.S., PA and [name] Dental Sleep Medicine, PLLC facilities data will be on a password protected computer with encrypted files to which [name] and research coordinator [name] may access.
- Transition from Research Participation - subjects are patients of record of the clinics.

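### The aim can be met by any one of many tests: no outcome, visit or contrast is primary, and no alpha or multiplicity rule is given

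*Combined protocol and SAP*

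**What the plan says.** The Purpose section sets out to compare two combination techniques and to find whether "either or both techniques improve tolerance to CPAP and/or are statistically more efficacious than CPAP or oral appliance therapy alone".

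The last paragraph of the Background says data will be collected at one month and at the end of two months, covering "AHI, CPAP pressure, and mask leakage, Nadir, T90, hours of usage and ESS". That is seven measures.

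Methods and Procedures randomises patients into "one of two groups (at least 25 each in each group"), and Criteria for Subject Selection gives "Number of subjects: 50-100". The analysis statement reads "Data will be analyzed quantitatively using, but not limited to, the Kolmogorov-Smirnov test", followed by Student's t test or the Wilcoxon rank-sum test. It does not link any test to an outcome or contrast.

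The month-1 and month-2 lists under Data Monitoring collect device data ("or Data card: CPAP pressure, leakage, AHi"), nadir and T90 from oximetry, two questionnaires, and an optional PSG or HST. Neither list includes hours of usage or ESS. The baseline list includes hours of usage but not ESS.

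**The concern.** The aim is satisfied by either technique, on tolerance or on efficacy, against either single therapy, and it sits beside a comparison of the two techniques. With nothing ranked, the result to be presented as the answer can be chosen after the data are seen. Followed as written, the plan lets one unadjusted p<0.05 out of many support a claim of statistical superiority, with an error rate well above 5%.

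Two features add to this. The contrasts with CPAP or oral appliance alone compare each patient with his or her own earlier therapy, without a concurrent control. And hours of usage, a natural measure of tolerance, has no scheduled collection at follow-up, although tolerance is half of the aim.

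**Working it through.** **The plan's own figure.** The only figure to reproduce is the 50–100 subjects. It cannot be reproduced, because no alpha, power, effect size or standard deviation accompanies it.

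**Inputs from the documents**
- Measures listed at both follow-ups: 5 (CPAP pressure, leakage, AHI, nadir, T90).
- Measures named in the Background: 7 (these plus hours of usage and ESS).
- Follow-up visits: 2. Arms: 2, at least 25 patients each.

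**Assumptions, none stated in the plan.** Two-sided 5% per test, parallel groups, no true effects. In the simulations: outcome correlation 0.3–0.7, baseline-to-follow-up correlation 0.5–0.7, month-1 to month-2 correlation 0.5–0.9. The questionnaires are not counted.

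**Test counts, derived from the schedule and the aim**
- Between arms, scheduled measures: 5 × 2 = 10.
- Between arms, Background measures: 7 × 2 = 14.
- Versus CPAP alone: 5 measures × 2 visits × 2 arms = 20.
- Versus oral appliance alone, if the baseline HST is the appliance verification test: 3 measures (AHI, nadir, T90) × 2 × 2 = 12.
- All contrasts on scheduled measures: 10 + 20 + 12 = 42.

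**Chance of at least one false positive.** For k independent tests it is 1 − 0.95^k:
- k = 10: 1 − 0.95^10 = 40.1%
- k = 14: 1 − 0.95^14 = 51.2%
- k = 42: 1 − 0.95^42 = 88.4%

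Correlation lowers these. Simulated results:

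| Family | Result |
|---|---|
| 10 between-arm tests, outcome correlation 0.3–0.7 | 20–36% |
| 14 between-arm tests, common correlation 0.3 / 0.5 / 0.7 / 0.8 | 43.8 / 34.8 / 24.9 / 19.8% |
| 42 tests, paired t within arm | about 60–82% |
| 42 tests, unpaired t within arm | about 22–46% |

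Over correlations from 0 to 0.8, the 14-test range is therefore about 20–51%. The 10- and 42-test rows are for 25 patients per arm. With 50 per arm, the 10-test and paired 42-test ranges are almost the same.

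**Regression to the mean.** Patients enter as partial responders because "the AHI was greater than or equal to 5 (verification sleep test"). If that same test is the oral-appliance-alone baseline, some fall in AHI on retest is expected with no treatment effect. Its size depends on the distribution and repeatability of AHI on the appliance. The documents give neither, so no figure is offered.

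**Detectable difference for one between-arm primary.** With 80% power, two-sided 5% and no dropout, the normal approximation is d = (1.960 + 0.842) × √(2/n):
- n = 25: 2.802 × 0.283 = 0.79 SD; noncentral t gives 0.81 SD.
- n = 50: 2.802 × 0.200 = 0.56 SD; noncentral t gives 0.57 SD.

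**The case against.** - **Visits and comparators are named.** A reader might infer that the plan has no time point or contrast at all. It has both; what is missing is a ranking among them.
- **The between-arm rate does not measure the stated aim.** The wording about superiority concerns each technique against a single therapy, whereas 20–36% describes one technique against the other. This stands. A between-arm p-value could not support the single-therapy claim even with only one test. The figure shows how loose one part of the plan is.
- **The 60–82% figure is not the plan as written.** It needs paired tests. The plan names Student's t, which may or may not mean paired, and the rank-sum test, which is unpaired. For favourable errors on the 32 single-therapy contrasts alone, paired tests give 28–46% and unpaired tests about 1–9%. The documents do not support quoting only the higher figures.
- **Regression to the mean may be absent.** The HST at study start may be a new test. Selection on an earlier verification test would then not bias that baseline. A reader might infer that an AHI gain over oral appliance alone would be an artefact, but the documents do not show this.
- **The AHI source is not fully open.** Device AHI is scheduled at both follow-ups, while PSG and HST are optional.
- **A crossover is a weak reading.** The Background phrase "they will use each one for two months" could suggest one, but the two groups in Methods and a schedule ending after month 2 indicate parallel arms.
- **The framing is partly exploratory.** The Purpose asks what the data suggest. An exploratory study may lack a primary, but this one never calls itself exploratory and does speak of statistical superiority.

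**Conclusion.** The gap is real: no primary outcome, visit or contrast, no alpha, no multiplicity rule, and an aim that any one of many results could meet. A single unadjusted p<0.05 would not be confirmatory.

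The percentages illustrate the problem and are not properties of the plan. They rest on the assumed 5% level, the derived test counts and the assumed correlations. For the two-visit between-arm families examined, the error is about four or more times the nominal 5%. How far the single-therapy contrasts raise the total is unsettled until the test is specified. Those contrasts are uncontrolled whichever test is used. Possible bias in the oral-appliance AHI contrast is conditional and cannot be sized.

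Separately, the Background and the visit lists disagree about hours of usage and ESS at follow-up, and ESS has no baseline.

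**What to change.** Before analysis:

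1. Name one primary outcome, visit, contrast and alpha. A suitable choice is the randomised contrast, CNMI versus preferred mask, at month 2, two-sided 5%, on an outcome the sponsor selects. If that outcome is AHI, take it from the device download for all patients.
2. If a formal claim against CPAP or oral appliance alone is kept, place it in a fixed test order with arm, comparator and outcome named. Use a paired test and state that the comparison is uncontrolled.
3. Report everything else with 95% confidence intervals as exploratory, and reword the Purpose so that its claim of statistical superiority matches.
4. Add hours of usage to the month-1 and month-2 lists, and add ESS at baseline, month 1 and month 2.
5. State the detectable difference for the between-arm primary: about 0.81 SD at 25 per arm and 0.57 SD at 50 per arm, at 80% power with no dropout.

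The cost is protocol wording, one more item from a device download already planned, and a questionnaire that the Background already promises at follow-up, plus its baseline. No patients are needed beyond the stated 50–100. The downside is that fewer results can be called significant, and the single-therapy claims become exploratory or sit lower in the test order.
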